Our proposed theory-derived intervention is guided by theoretical constructs from the self-efficacy theory. Self-efficacy, one's confidence in the ability to perform particular behaviors, influences the performance of those behaviors, which in turn impacts health outcomes. Enactive mastery experiences, verbal persuasion, vicarious experiences, and physiological/ emotional status are the four principle sources of self-efficacy beliefs. Evidence illustrates that physical activity interventions designed based on self-efficacy concepts

effectively promote physical activity in older adults. The personalized behavioral intervention, which includes physical activity training, exercise prescription, goal setting, phone coaching, consultation, and feedback, real-time physical activity self-monitoring, interactive prompts and feedback with smartwatch, and weekly financial incentives will provide older adults with a stronger sense of self-efficacy. This will engage them in physical activity.

4. Study Procedures

Overview of study design: This is a two-group randomized controlled trial to test the effectiveness of a 12-week personalized behavioral intervention implementing smartwatch technology in promoting physical activity, pain, and sleep in older adults in comparison with a control group. We aim to enroll 20 eligible participants in one years and complete the study in 18 months. Length of a subject's participation time in study will be 16-18 weeks in total, which includes 2-3 week of screening and pre-intervention data collection, 12-week intervention/control period, and 2-3 week post-intervention data collection. It is an unblinded trial. Due to the nature of the intervention (ongoing communication between research team and participants), it is impossible to blind the group assignment from the participants and the research team.

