Self-monitoring: Subjects will self-monitor their level of physical activity (steps & minutes of moderate activity) using the smartwatch. The Google calendar and Fitbit apps will send messages and alerts to the subject's smartwatch that encourage them to achieve their daily goals. For example, a participant may typically be inactive for a long period (e.g., >90 minutes) at 10AM. In this case, the research assistant will program the smartwatch to pro-actively chime or vibrate at 10AM each day with a reminder message through Google Calendar. Similarly, if the smartwatch detects a long sedentary period, the Fitbit app will automatically send an alert via the smartwatch to motivate the subject to increase their physical activity. The smartwatch will be removed every 3-4 days for charging. If a participant has low activity for 3 consecutive days, the research assistant will call the participant to either encourage them to adhere to the plan or provide a modified plan after consulting the exercise trainer.

Phone consultation: Subjects will have biweekly phone consultation with the research team members to receive guidance and adjustment on activity plans. Recognizing that changing behavior is a process, the personalized activity plan will be less intense at the beginning and adjusted every two weeks based on participant's data during the previous two weeks.

Description of control condition: The control group will receive general education on physical activity for older adults and continue their daily activity and healthcare routine. They will also receive a Go4Life program book from the National Institute on Aging.

Data collection includes pre-intervention (baseline, 2weeks) and post-intervention (2weeks). The data collection will take place in a private room at the School of Nursing, a clinic office or the participant's apartment per the participant's preference.

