Baseline data collection: After randomization, the research team will distribute an Actigraph to each eligible participant and instruct them to wear it on his/her non-dominant wrist day and night for 14 consecutive days. At the same time, the participants will be instructed to fill out a two-week sleep diary during the days they wear the Actigraph. Pre-intervention (baseline) data collection will take about 45-60 minutes. A research team member will interview eligible participants (up to 30 minutes) for age, race, education, height, weight, life style (tobacco & alcohol use), depression, pain, fatigue, self-reported physical activity, Activity of daily living, self-reported sleep quality, pain, medication use (antidepressant, benzodiazepine, pain and sleep medication), and medical conditions. The research assistant with Phlebotomy training will collect blood sample (5-10ml) from participants.

Post-intervention data collection: After the intervention or control period, a research team member will mail an Actigraph and a two-week sleep diary to the participant's home and contact the participants by phone to provide instructions. The participant will wear the Actigraph and fill out the sleep diary for 2 weeks. A research team member will schedule a meeting with the participant after the Actigraph session to collect post-intervention data. At the meeting, the participants will provide blood sample and be assessed for pain, depression, level of physical activity, and other measures that were collected at screening and pre-intervention following the same procedures. In addition, the participant will be interviewed individually for his/her perspective and experience of the intervention at the meeting for post- intervention data collection. The conversations will be audio recorded and field notes will be taken by a research team member during the interview. We estimate each interview will last no more than 30 minutes. The participant will be asked to answer open-ended questions about the participant's experience of working with smartwatch and the intervention. The voice recordings will be sent to the Production Transcripts for transcription (<https://www.productiontranscripts.com/>). Production Transcripts is a full-service transcription company that specializes in medical and academic research and has a BAA with Johns Hopkins.

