PROMIS measures will be used to assess multiple study outcomes. NINR Common data element of sleep, fatigue, anxiety, depression and cognition If a participant is significantly depressed (rating “Always” in all the 6 items that assess depressive symptoms) and not receiving any treatment for depression during assessments, we would share the information with the participant’s primary care provider and refer the participant for treatment with his/her primary care provider.

Functional Status: We will use the Katz Index of Independence in Activities of Daily Living (ADL) and The Lawton Instrumental Activities of Daily Living (IADL) Scale to measure older adult’s functional status.

Balance and gait speed will be measured using the Short physical performance battery (SPPB)

Other information includes age, race, body mass index, education, life style (tobacco and alcohol use, BMI), depression (GDS), pain, fatigue, medication use (antidepressant, benzodiazepine, pain and sleep medication), and number of medical conditions. Information will be collected via questionnaires.

The study will not interfere with the participants’ routine care. Participants in both groups will receive their routine care. The participants at both groups have the freedom to withdraw anytime from the study. The research team will remove the participants from the study if the research team cannot get contact with the participants for a month or the participant miss two appointments with the research team for no reason.

5. Inclusion/Exclusion Criteria

Key inclusion criteria include 60-85 years, intact cognition [[Montreal Cognitive Assessment \(MoCA\)>23](#)], poor quality of sleep (Insomnia Sleep Index>7), self-reported presence of pain, capacity for mild to moderate physical activity.

Participants will **be excluded** if they 1) have serious underlying illness (such as malignant neoplasms, infection, unexplained fever, weight loss, or recent trauma) causing their pain, 2) are non-ambulatory or have severely impaired mobility, 3) have visual or hearing impairment that interfered with assessments, and 4) have an acute or a terminal illness, 5) have neuropathic pain.

6. Drugs/ Substances/ Devices

N/A

7. Statistical analysis plan (SAP)

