7.1. Sample characteristics: We will compare the values of demographic and baseline clinical variables between the two study arms using t-tests or Mann-Whitney U-tests for continuous variables and chi-squared or Fisher’s exact tests for categorical measures. This analysis will both describe the overall study sample and confirm that randomization resulted in the expected balance between covariates of interest;

7.2 Descriptive analysis will be used to describe the feasibility data;

7.3 Preliminary efficacy: Repeated Measures ANOVA will be performed to examine if the proposed intervention increases the participants’ proposed outcomes compared to the control arm. Analyses will examine the interaction (Time × Group) to access whether there are differences in changes in outcome variables between the two arms. The initial effect size of the intervention will be determined based on results of pain outcomes.

8. Risks

Minimal risks to study participants are expected. There is minimal risk associated with physical activity. We will explain associated risk to the participants. In very rare occasions, the subject may fall or get

injured during physical activities. These adverse events should be minimized by using personalized physical activity plans, which will be developed/designed by the exercise trainer to be most suitable for the subject based on the subject's personal features. Some environmental factors (e.g. weather) may impact on the participant's safety when they perform physical activity outside. We will advise participants of this safety information during the exercise intervention. For example, we will advise them to perform indoor physical activities in the following weather conditions: temperature lower than 32°F or higher than 90°F, rainy, snowy or heavy windy weather. We will also advise them to hydrate during performing physical activity and hot weather. The activity intervention will be based on an existing NIH-funded activity protocol for older adults. Finally, the study participant's primary care provider will be contacted to confirm that the study participant can safely engage in the activity regimen.

Subjects may experience psychological reactions to completing the questionnaire data and cognitive tests. Since the questions are benign, the risk is minimal.

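### With one pre and one post value, the section 7.3 Time × Group test is a change-score t-test: valid, but usually less precise at N = 20 than ANCOVA; and the section 7.1 tests cannot confirm balance

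*Combined protocol and SAP*

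**What the plan says.** The combined protocol and SAP gives the assessment schedule in section 4 (Study Procedures): "Data collection includes pre-intervention (baseline, 2weeks) and post-intervention (2weeks"). No outcome assessment in between is described. The sample size is in the same section: "We aim to enroll 20 eligible participants in one years and complete the study in 18 months". Allocation is 1:1 in blocks of 4, so five full blocks give 10 per arm.

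Section 7.3 sets the efficacy analysis: "Repeated Measures ANOVA will be performed to examine if the proposed intervention increases" the outcomes relative to control. The tested term is the Time × Group interaction, and no baseline covariate is named. The same section makes the estimate a product of the trial: "The initial effect size of the intervention will be determined based on results of pain outcomes".

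Section 7.1 compares baseline variables between arms with t-tests, Mann-Whitney, chi-squared or Fisher tests. It says this will describe the sample and also "confirm that randomization resulted in the expected balance between covariates of interest".

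Three other statements in section 4 bear on the point. On baseline collection: "After randomization, the research team will distribute an Actigraph to each eligible participant". On masking: "It is an unblinded trial". On attrition: "The research team will remove the participants from the study" after a month without contact or two unexplained missed appointments.

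**The concern.** With two occasions and two arms, the interaction test uses the baseline only by subtracting it, which fixes the slope of post on baseline at 1. If the true slope is lower, subtraction over-corrects: a chance baseline difference D between arms moves the estimate by (slope − 1) × D. With 10 per arm such differences are common. ANCOVA estimates the slope and removes that shift, using data the trial already collects.

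What is at stake is the precision and reliability of the initial effect size, which 7.3 names as an output. Type I error is not at stake, and no decision rule in the documents depends on the result.

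The second issue is inference from 7.1. A non-significant baseline test at this sample size is weak evidence of similarity, and a significant one under proper randomisation is chance. Reading the tests as confirmation of balance gives false reassurance, and 7.3 then makes no ANCOVA-type adjustment for an imbalance that 7.1 probably missed.

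**Working it through.** **Inputs.** From the documents: N = 20, 1:1 allocation, one pre and one post collection, Time × Group interaction. The documents give no α, SD, pre-post correlation ρ, power or dropout, so there is no plan figure to reproduce. Assumed: bivariate normal outcome, baseline SD 1, post SD equal unless stated, two-sided 5%, n = 10 per arm.

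**1. Identity.** For complete pairs with one value per period, the interaction F on (1, 18) df equals the squared pooled t on post minus baseline. Check on one simulated 10 versus 10 data set: F = 3.9596, t² = 3.9596.

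**2. Precision with equal SDs (slope = ρ).**

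- Change score: Var = (2/n) × 2(1 − ρ), 18 df.
- ANCOVA: Var = (2/n)(1 − ρ²) × (1 + 1/(N − 4)) = (2/n)(1 − ρ²) × 17/16, 17 df.
- Variance ratio, ANCOVA to change = (1 + ρ)/2 × 17/16.

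Example at ρ = 0.5: the change-score variance is 0.2 × 1 = 0.200 (SE 0.447, half-width 0.94). The ANCOVA variance is 0.2 × 0.75 × 17/16 = 0.159 (SE 0.399, half-width 0.84).

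| ρ | Variance ratio | Half-width, change (SD) | Half-width, ANCOVA (SD) | Width ratio |
|---|---|---|---|---|
| 0.3 | 0.69 | 1.11 | 0.93 | 0.835 |
| 0.5 | 0.80 | 0.94 | 0.84 | 0.896 |
| 0.7 | 0.90 | 0.73 | 0.70 | 0.954 |
| 0.8 | 0.96 | 0.59 | 0.58 | 0.982 |
| 0.9 | 1.01 | 0.42 | 0.42 | 1.009 |
| 0.95 | 1.04 | 0.30 | 0.30 | 1.022 |

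Break-even on variance: ρ = 32/17 − 1 = 0.88. On interval width, with the change from 18 to 17 df, it is 0.87.

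Simulation of 100,000 trials per setting agrees: mean width ratios are 0.832, 0.895, 0.953, 0.981, 1.007 and 1.021 at the same ρ. Rejection under the null was 0.049 to 0.052 for both analyses.

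**3. Power at a true difference of 0.8 SD** (40,000 trials per setting), change versus ANCOVA: 0.30 versus 0.40 at ρ = 0.3; 0.39 versus 0.47 at 0.5; 0.59 versus 0.63 at 0.7; 0.97 versus 0.96 at 0.9.

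**4. Sensitivity (simulated).**

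- 8 completers per arm: ANCOVA is 16%, 10%, 4% and 1% narrower at ρ = 0.3, 0.5, 0.7 and 0.8, and 2% wider at 0.9.
- Post SD 0.8 × baseline, ρ = 0.5/0.7/0.9: 22%/18%/19% narrower.
- Post SD 1.2 × baseline, same ρ: 4% narrower/2% wider/2% wider.

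**5. Chance imbalance and the 7.1 tests.** D has variance 2/10 = 0.2, so P(|D| > 0.5 SD) = 2 × (1 − Φ(0.5/√0.2)) = 0.264. For p < 0.05 the observed gap must reach 2.101 × √0.2 = 0.94 pooled SD. Of the trials with a gap above 0.5 SD, the t-test is non-significant in 81% (rough check: 1 − 0.05/0.264 = 0.81).

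**6. Coverage of the nominal 95% change-score interval when |D| > 0.5 SD:** 0.883, 0.905, 0.921, 0.929 and 0.942 at ρ = 0.3, 0.5, 0.7, 0.8 and 0.9. ANCOVA: 0.948 to 0.950. In the other 74% of trials the change-score interval over-covers, at 97.2%, 96.5%, 96.1%, 95.7% and 95.4%. At ρ = 0.3 the average is 0.264 × 0.883 + 0.736 × 0.972 = 0.95, as it should be.

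**The case against.** The strongest reply is that 7.3 contains no error. It asks whether change differs between arms, a change-score test answers that with correct size, and efficacy is only preliminary in a 20-person pilot. That stands as a limit on severity, not as a reason to keep the less precise estimator when the effect size is a stated output.

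Four narrower points also stand:

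- **The gain depends on an unknown ρ.** It is small at 0.7 to 0.8 and absent above about 0.87. In a single trial ANCOVA gives the wider interval in 10%, 20%, 37%, 49% and 64% of runs at ρ = 0.3, 0.5, 0.7, 0.8 and 0.9.
- **Narrower and imbalance-corrected do not always come together.** When |D| > 0.5 SD, the mean width ratio is 0.88, 0.94, 1.00, 1.03 and 1.06 at those ρ. In those trials, though, the change-score interval under-covers, and ANCOVA still has the smaller root mean squared error up to about ρ = 0.87 with equal SDs (0.346 versus 0.390 at 0.7).
- **The insomnia index is both an outcome and an entry criterion (above 7)**, which restricts its baseline spread. If entry cut at the median of the underlying distribution (an assumption), ANCOVA would be 2% narrower, equal, and 1% wider at underlying ρ of 0.5, 0.7 and 0.8. This has not been shown for pain, the source of the effect size.
- **The identity needs one value per period.** The documents do not say how the 14 Actigraph nights are summarised; a single summary is the natural reading.

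On 7.1, describing the sample is a proper purpose and no later step uses the p-values. Only the inference of balance fails.

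**Conclusion.** The concern holds, as a precision point that should be addressed rather than a validity error. The planned test is a change-score t-test with correct type I error and correct coverage averaged over all trials.

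With ρ unknown, the balance favours ANCOVA. Across the settings examined it gains up to about 20% in interval width and loses at most 2 to 3%. All these sizes rest on the normal model and assumed correlations and SDs. The 7.1 claim to confirm balance cannot be supported at 10 per arm.

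Both analyses share a caveat. Actigraph baseline wear starts after an unmasked allocation, so knowledge of the arm could shift the baseline. Such a shift would enter the change score in full and ANCOVA multiplied by the slope; neither removes it.

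**What to change.** - **Section 7.3.** Replace the repeated measures ANOVA with text such as: *For each continuous outcome, the post-intervention value will be modelled on arm and the baseline value of that outcome; the adjusted difference will be reported with a 95% confidence interval, and participants will be analysed in the arm to which they were allocated.* Define the single Actigraph summary per period. State that the model uses participants with an observed post value, and report by arm how many have none and why.
- **Section 7.1.** Drop the between-arm p-values and the claim about confirming balance. Report descriptive statistics by arm.
- **Section 4.** Collect baseline (Actigraph, diary, interview) before allocation. If that cannot change, state it as a limitation of either analysis.

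**Cost.** The 7.1 and 7.3 changes are SAP wording and need no extra data. ANCOVA spends one residual degree of freedom (18 to 17) and carries a variance factor of 17/16, about 6%, so it is slightly worse if the true slope is close to 1. Moving baseline changes the order of procedures, not the amount of data.

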Study Protocol and Statistical Analysis Plan

Title: A Personalized Behavioral Intervention for Older Adults with Musculoskeletal Pain and Sleep Complaints

NCT03921840

Date: 9/1/2020

1. Abstract

It is well recognized that physical activity/exercise is an effective intervention to improve sleep, reduce pain and improve function in a variety of pain conditions. Traditional interventions to increase physical activity are challenging in older adults due to extensive staffing requirements and low adherence. We plan to conduct a pilot trial in a cohort of older adults (without dementia) with both chronic musculoskeletal pain and nocturnal sleep complaints to test the effectiveness of a 12-week personalized behavioral intervention (compared to a control group) embedded within a smartwatch application in older adults. 20 cognitively intact elders will be enrolled and randomly allocated to intervention or control group. Participants in the intervention arm will receive a 2-hour in person education session, and personalized, circadian-based activity guidelines, with real time physical activity self-monitoring, interactive prompts, biweekly phone consultation with the research team, and financial incentives for achieving weekly physical activity goal. The control group will receive general education on physical activity in older adults and continue their routine daily activity for 12 weeks.

2. Objectives

This study aims to examine 1) the feasibility and acceptability of a personalized behavioral intervention implementing mobile health technology for promoting pain, sleep, and mood in older adults with chronic pain and sleep complaints. 2) The preliminary efficacy of the study on pain and sleep outcomes

3. Background

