Screening (30minutes): After informed consent, the research team will assess (maximum of 30 minutes) the participants' eligibility for intact Cognition using the Montreal Cognitive Assessment (MOCA) and poor sleep quality by asking "do you have problems with your sleep? Do you feel refreshed after sleep?", and pain by asking "Are you currently troubled by physical pain, either all the time or on and off? Has this pain persisted for at least 3 months?", and readiness for performing regular exercise using the physical activity readiness questionnaire (PAR-Q). Participants who passed the PAR-Q are eligible for participation. For those who failed to pass the PAR-Q, medical clearance along with information about specific exercise limitations needs to be obtained from their primary care providers in order to participate. People who fail to pass the screening will drop the study after the screening process.

Randomization: Eligible participants will be randomly allocated to either intervention or control group (1:1) using blocked randomization with a block size of 4. A computer-based assignment scheme will be used to determine the participant's group assignment.

Intervention description: Based on the self-efficacy theory, participants in the intervention arm will receive personalized, circadian-based activity guidelines, 2 or 3 1-hour in person education session, real time physical activity self-monitoring, interactive prompts, biweekly phone consultation with the research team, and financial incentives for achieving weekly physical activity goal.

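### The two-visit repeated-measures ANOVA in section 7.3 uses only participants with both values, which can bias the Time × Group estimate and the effect size taken from it

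*Combined protocol and SAP*

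**What the plan says.** Section 7.3 gives the method: "Repeated Measures ANOVA will be performed to examine if the proposed intervention increases the" outcomes compared with the control arm. The test is then specified: "Analyses will examine the interaction (Time × Group) to access whether there are differences in changes in outcome variables between the two arms". The same section takes the initial effect size of the intervention from the pain outcomes.

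The Data collection paragraph of section 4 sets two outcome occasions and no visit between them: "Data collection includes pre-intervention (baseline, 2weeks) and post-intervention (2weeks"). The abstract says "20 cognitively intact elders will be enrolled and randomly allocated to intervention or control group", and the Randomization paragraph has participants "randomly allocated to either intervention or control group (1:1) using blocked randomization with a block size of 4".

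Two routes to a missing post-intervention value appear at the end of the Measurement part of section 4. One is voluntary: "The participants at both groups have the freedom to withdraw anytime from the study". The other is removal by the team, after a month without contact or two missed appointments without a reason.

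Baseline is measured late: "After randomization, the research team will distribute an Actigraph to each eligible participant".

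The documents name no analysis set, intention-to-treat rule, missing-data assumption, imputation, sensitivity analysis or expected dropout. The only text on missing data, under Data management, concerns weekly data-entry queries.

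**The concern.** With two occasions, a classical repeated-measures ANOVA needs complete pairs. A participant with a baseline and no post-intervention value drops out of 7.3 altogether, although the baseline comparison in 7.1 can still use that baseline. The plan does not say that it analyses completers; this follows from the method it names.

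The Overview presents the study in these terms: "This is a two-group randomized controlled trial to test the effectiveness" of the programme. The comparison of interest is therefore between the arms as randomized. The arms differ in scheduled contact. The intervention arm has two or three training sessions, biweekly calls, and further calls after three consecutive low-activity days. The control arm has general education and a book. A removal rule based on contact and appointments has more occasions to act in the intervention arm, so unequal and selective loss is plausible, though not documented.

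At stake is the effect size for pain, which 7.3 names as a product of the pilot. With 10 per arm, two or three leavers are 20% to 30% of an arm.

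**Working it through.** **Inputs from the documents.** Two outcome occasions; 20 randomized 1:1 in blocks of 4, so 20/4 = 5 full blocks and 10 per arm. The documents give no dropout rate, correlation, SD or target effect. Those below are assumptions, in SD units, with pain scored so that higher is worse.

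**Step 1: what the interaction estimates.** With two occasions, the Time × Group contrast is (mean post − mean pre) in the intervention arm minus the same in control, and its F equals the squared two-sample t on change. In a simulated data set of 20 with 4 post values deleted, F = 0.9519 and t² = 0.9519, both from the 16 complete pairs. The four baselines without a post value have no influence.

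**Step 2: when loss linked to baseline severity biases it.** Let r be the pre-post correlation and δ the true reduction. Then post = r × baseline − δ × arm + error, so change = −(1 − r) × baseline − δ × arm + error. If completers' mean baseline is shifted by m_I in the intervention arm and m_C in control, the contrast is

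−δ − (1 − r)(m_I − m_C).

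The bias depends on m_I − m_C. The same mechanism in both arms gives m_I = m_C and no bias. Simulation with about 20% loss agrees: the bias is zero to within 0.002 SD when loss rises with severity equally in both arms.

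**Step 3: size under unequal loss.** Assume δ = 0.50, 25% intervention loss rising with baseline severity, and 10% random control loss (m_C = 0). Take a steep link, with the odds of leaving up about 4.5-fold per SD of severity (log-odds slope 1.5). Leavers then average 0.83 SD worse at baseline.

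- m_I = −0.25 × 0.83 / 0.75 = −0.277
- r = 0.4: bias 0.6 × 0.277 = 0.166; effect 0.50 − 0.166 = 0.33
- r = 0.6: bias 0.4 × 0.277 = 0.111; effect 0.50 − 0.111 = 0.39

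| Severity link (intervention arm) | Planned contrast, r = 0.4 to 0.6 | Likelihood model, all baselines |
|---|---|---|
| Log-odds slope 1.5 per SD (simulated, 10 per arm) | 0.34 to 0.39 | 0.50 |
| Log-odds slopes 0.5 to 1.0 per SD (simulated, 10 per arm) | 0.37 to 0.45 | 0.50 |

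The likelihood model evaluates the regression of post on baseline at the mean of all baselines in the arm, which removes m_I. It does so with or without a common baseline mean across arms.

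**Step 4: where the likelihood model does not help.**

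- *Loss tied to the unseen post value, in one arm only.* With about 20% loss, a true effect of zero and r = 0.3, 0.5, 0.7, the ANOVA is biased by −0.11, −0.08, −0.05 and the likelihood model by −0.15, −0.13, −0.09. With a true effect of 0.50 and the Step 3 loss rates and correlations, the ANOVA gives 0.55 to 0.67 and the likelihood model 0.58 to 0.74.
- *Disengagement.* If a fraction p of the intervention arm gets no benefit and is lost, completers show δ while all randomized show (1 − p)δ, a ratio of 1/(1 − p). For p = 0.20 the ratio is 1.25. For p = 0.30 it is 1.43, or 0.50 against 0.35. The likelihood model also returns 0.50. Giving the missing participants the control-arm mean change returns 0.7 × 0.50 + 0.3 × 0 = 0.35.

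**Step 5: precision.** The 95% half-width is t × √(2(1 − r)) × √(1/n + 1/n). At r = 0.5, 10 per arm gives 2.101 × 1 × 0.447 = 0.94 SD, and 8 per arm gives 2.145 × 1 × 0.5 = 1.07 SD.

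**The case against.** The strongest reply is that unequal loss is assumed. Section 4 grants the freedom to withdraw but predicts no rate. Section 10 could favour retention in the intervention arm: both arms receive $50 after post-intervention data collection, but only the intervention arm can earn up to $60 more and keep the Fitbit on completion. This stands. Neither the direction nor the size of differential loss can be read from the documents.

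The severity link also matters. The low end of the illustrated range needs a steep one. With an odds ratio of 2 per SD the bias is 0.10 (r = 0.4) or 0.06 (r = 0.6), and with 1.5 it is 0.06 or 0.04. All of these are small beside a half-width near 1 SD in a pilot whose efficacy aim is labelled preliminary. That stands as a limit on the consequence. It does not justify the method, because the point estimate is what 7.3 carries forward.

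A reader might infer that the plan will certainly give a biased effect, or that loss would pass unnoticed. Neither is supported. Step 2 shows when bias is absent. Section 7.2 describes feasibility data and section 8 has retention and completeness monitored, although counts by arm beside the efficacy estimates are not promised.

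A reader might also take the 43% inflation under disengagement as an argument for the mixed model. It is not: the mixed model gives the same answer as completers there.

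**Conclusion.** The point holds as a conditional one. Section 7.3, as written, is a complete-pairs analysis and can misstate the effect of being assigned to the programme. Under the assumed 25% and 10% losses and correlations of 0.4 to 0.6, a true 0.50 SD averages 0.34 to 0.45 SD, a shortfall of 0.05 to 0.16 SD. A likelihood model keeping all baselines removes this. If loss follows the unseen outcome or disengagement, the planned analysis overstates the effect instead. The likelihood model does not repair that and can do worse, so it is not sufficient alone.

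The reading that all 20 can be analysed also goes too far. Baseline follows randomization, so an early leaver may have no outcome value at all.

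**What to change.** In 7.3, replace the repeated-measures ANOVA with a likelihood-based mixed model for the two time points. Include every randomized participant with at least one outcome value, in the arm assigned, and keep the Time × Group term as the effect of interest. State that this estimate assumes data missing at random.

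Add one sensitivity estimate in which missing intervention-arm outcomes take the control-arm mean change. Report the number missing by arm beside each estimate, including the effect size for pain.

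The cost is a few sentences in the SAP and one extra model run, with no new data. The downsides are reliance on the missing-at-random assumption for the main estimate, and that early leavers without a baseline still cannot enter the model.
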